7.9. Multiple Assessments and Visit Windows

Nominal visits (e.g., those identified by the study eCRF) will be the basis of summarization and statistical analysis; no visit date windowing will be conducted. Unless specified otherwise, data from unscheduled visits will be included in: (1) summaries of most extreme and baseline data, (2) summaries of specific abnormalities at any time post-baseline, (3) adverse events and any other summaries not based on study visit, (4) subject data listings, and (5) analyses that utilize MRI-PDFF, PK, lipidomic/metabolic biomarkers, collagen/fibrous area and fibrosis score assessed by digital pathology, SNPs relevant for NASH, and PRO-C3 data where unscheduled visit results may be used in analyses at the closest scheduled visit; if the closest scheduled visit already has valid MRI-PDFF data then the unscheduled visit results will not be used in the analysis.

7.10. Handling of Early Termination Visit Information

If a subject is terminated early from this study the early termination visit data will be analyzed at the closest scheduled visit. If the closest visit has valid data, the early termination data will be assigned to the next available visit.

7.11. Missing Data

Imputation will only be performed on the primary and selected secondary efficacy endpoints based on histological and MRI-PDFF data. Imputed data will be analyzed using both the ITT and mITT populations.

For the primary efficacy endpoint and secondary efficacy endpoints based on histology, a subject who discontinued treatment prior to Week 42, does not provide a histological assessment on or after Week 42, or who otherwise has missing data will be considered a non-responder. A pre-specified sensitivity analysis of the primary efficacy endpoint will employ the multiple imputation technique.

For the secondary endpoint $\text{MRI-PDFF} \geq 30\%$ responder analysis at Week 26, a subject who discontinued treatment prior to Week 20, does not provide an MRI-PDFF assessment between Week 20 through Week 27, or who otherwise has missing data will be considered a non-responder. For analysis of MRI-PDFF, missing data at Week 26 will be imputed using the last post-baseline observation obtained at least 20 weeks to 27 weeks after the first dose. For the $\text{MRI-PDFF} \geq 30\%$ responder analysis at Week 52, a subject who discontinued treatment prior to Week 42, does not provide an MRI-PDFF assessment after Week 42 or who otherwise has missing data will be considered a non-responder. Missing data at Week 52 will be imputed using the last post-baseline observation obtained at least 42 weeks after the first dose. These missing data techniques will also be applied to $\text{MRI-PDFF} \geq 50\%$ responder analyses.

Additional details are provided in the relevant analysis sections below.

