- Change from Baseline in FGF-21, adiponectin, and other NASH biomarker levels at Weeks 26 and 52 and at each study visit. This secondary endpoint will be analyzed similarly to MRI-PDFF percent change and change from Baseline at Week 26, as described above.
- Change from Baseline in FibroScan and CAP score results at Weeks 26 and 52. This secondary endpoint will be analyzed similarly to MRI-PDFF percent change and change from Baseline at Week 26, as described above.

- Change from Baseline in PRO-C3 and other fibrosis biomarkers at Weeks 4, 13, 26, and 52. This secondary endpoint will be analyzed similarly to MRI-PDFF percent change and change from Baseline at Week 26, as described above.
- Change from Baseline in ELF score at Weeks 26 and 52. This secondary endpoint will be analyzed similarly to MRI-PDFF percent change and change from Baseline at Week 26, as described above.

The analysis of the primary and secondary endpoints will be carried out for the ITT analysis set and repeated for the mITT analysis set.

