In the event a subject is unable to complete the end of treatment MRI-PDFF and/or liver biopsy within the protocol-specified window (Week 52 +/- one week), extended dosing is permitted to maintain continuous dosing up to the time both assessments are completed, to a maximum total of 56 weeks of dosing. In this instance, the Follow-up visit at Week 56 for post treatment safety and efficacy assessments is to be adjusted to occur four weeks after the last dose (+/- one week).

In the instance of a dose hold due to an AE or SAE, the decision to resume study drug will require consultation with the Investigator, the CRO's Medical Monitor, and the Sponsor's Chief Medical Officer.

Improvement of NAS and improvement of fibrosis score will be evaluated by comparison of Baseline and Week 52 liver histology specimens. Subjects will also undergo MRI-PDFF prior to the start of treatment, at Week 26, and at Week 52 or Early Termination unless it presents a logistical or physical hardship to the subject. MRI-PDFF is not required at Early Termination if a subject has completed less than 22 weeks of study treatment. Other efficacy and pharmacodynamic (PD) assessments include FibroScan with CAP, and measurement of liver aminotransferases, lipid parameters, and other noninvasive biomarkers of NASH and liver fibrosis throughout the study.

During the study, safety will be assessed by vital signs, 12-lead electrocardiograms (ECGs), physical examinations including eye examinations, and clinical laboratory testing. Subjects will be evaluated for AEs and concomitant medication use throughout the study.

Blood samples will be collected at Baseline (Day 1) and at Weeks 4, 13, 26, and 52 for the assessment of sparse PK. In addition, blood samples will be collected on Day 1 and at Week 4 from a subset of subjects for serial PK.

An independent data monitoring committee (IDMC) will be established by charter to provide independent review and assessment of study data and to monitor the overall study conduct in a systematic manner to safeguard the safety of study subjects. The IDMC will be tasked with making recommendations to the Sponsor to continue, amend, or stop the study based on these assessments.

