6. ANALYSIS POPULATIONS/SETS

Intention-to-Treat (ITT) Population: The principal analysis of the primary and secondary efficacy endpoints will be based on the Intention-to-Treat (ITT) population, which comprises all randomized subjects; this population will serve as the basis for all efficacy analyses. Subjects' data will be analyzed according to their randomized treatment assignment.

Modified Intention-to-Treat (mITT) Population: Comprises all subjects in the ITT population who have completed at least 42 weeks of treatment and have an evaluable post treatment histological assessment. Subjects will be analyzed according to the randomized treatment assignment.

Interim Analyses Modified Intention-to-treat (IAmITT) Population: Comprises a subset of approximately 60 subjects in the ITT population with 8% \geq MRI-PDFF at screening or at baseline with at least 1 evaluable post-Baseline MRI-PDFF value, defined as an MRI-PDFF assessment obtained at least 22 weeks after the first dose of study drug.

Safety (SAF) Population: Consists of all randomized subjects who received at least 1 dose (partial or complete) of study drug. This population will be used for all summaries of subject accountability, demographic and baseline data, and safety information, including AE incidence, clinical laboratory data, ECG data, and vital signs data. Subjects' data will be summarized according to the treatment they received. If all subjects were dosed according to randomized treatment assignment, then the safety and ITT analysis sets are identical.

PK Population: Comprises all ITT subjects with available PK measurements.

Serial PK Population: Comprises the subset of subjects who provided blood samples for evaluation of serial PK at timepoints on Day 1 and at Week 4.

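### The supportive mITT repeat of the Week 26 MRI-PDFF responder analysis selects subjects on treatment and biopsy events that usually fall 16 to 26 weeks after the scan

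*SAP*

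**What the plan says.** SAP 7.11 limits the scope of imputation: "Imputation will only be performed on the primary and selected secondary efficacy endpoints based on histological and MRI-PDFF data". It then names the populations: "Imputed data will be analyzed using both the ITT and mITT populations". The same section sets the Week 26 rules. For the responder endpoint (endpoint 2 in SAP 7.4), a subject is a non-responder if treatment stopped before Week 20 or if the subject "does not provide an MRI-PDFF assessment between Week 20 through Week 27". For the MRI-PDFF values, "missing data at Week 26 will be imputed using the last post-baseline observation obtained at least 20 weeks to 27 weeks after the first dose". Nothing takes Week 26 out of the mITT repeat.

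Protocol 13.2.2 points the same way for all primary and secondary endpoints: the analysis is "carried out for the ITT analysis set and repeated for the mITT analysis set".

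SAP 6 defines mITT as the ITT subjects "who have completed at least 42 weeks of treatment and have an evaluable post treatment histological assessment". ITT is the principal population for primary and secondary efficacy endpoints (SAP 6, Protocol 13.4.2.1).

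SAP 9.2 differs. It names ITT and mITT for the other histological responder endpoints, only ITT for the ANCOVA of change at a single visit, and no population for the MRI-PDFF responder endpoints.

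**The concern.** The mITT set is built for Week 52 histology. Applied to a Week 26 scan, it selects on the future. A subject with a valid Week 26 scan who stops drug at Week 30, or who completes treatment but declines the biopsy, drops out of the Week 26 result.

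This is more than lost precision. If later leaving is related to the Week 26 response, and related differently in the two arms, the mITT difference moves away from the ITT difference for reasons unrelated to the effect at Week 26. A reader comparing the two tables could not tell whether a gap came from missing Week 26 data, which is what a supportive repeat should probe, or from what happened afterwards.

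**Working it through.** **Timing of selection** (SAP 6, 7.11 and 4.1)

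- Week 26 to the 42-week treatment condition: 42 − 26 = 16 weeks.
- Week 26 to the scheduled biopsy: 52 − 26 = 26 weeks.
- Week 26 to the latest biopsy, given that dosing may be extended "to a maximum total of 56 weeks of dosing": 56 − 26 = 30 weeks. This is a maximum, not the usual gap.

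The Schedule of Assessments (Protocol Table 2, footnote on histology) requires an end-of-study biopsy after early termination only if at least 42 weeks of treatment were completed. Anyone stopping between Weeks 26 and 41 is therefore outside mITT, whatever the Week 26 scan showed. SAP 11 lists no change that removes the mITT repeat.

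**The planned dropout figure**

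The plan's sample size reproduces with an unpooled normal approximation (40% vs 20%, one-sided 0.05, 80% power, 2:1): placebo n = (0.2 × 0.8 + 0.4 × 0.6/2) × (1.645 + 0.842)² / 0.2², which rounds up to 44. The total is 132, and 132/(1 − 0.185) = 162. The 18.5% is thus about 0.185 × 162 = 30 subjects.

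**How many scans could be lost**

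The documents do not time the dropout. If a quarter to three quarters of it falls after the Week 26 scan (assumption), that is about 7 to 22 subjects. This is an upper-end count of lost scans. Some sites do no MRI-PDFF, the scan is optional on hardship, and endpoint 2 needs Baseline liver fat of at least 8%.

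**How far the Week 26 difference could move**

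Assumptions, none given in the documents: true rates of 55% vs 15%; 10% of each arm leaving after the scan; relative risk of leaving k for non-responders against responders, with k = 3 or 1/3.

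Risk of leaving in responders: q = 0.10/(p + (1 − p)k). Rate among those retained: p(1 − q)/0.90.

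| p | k | q | retained rate |
|---|---|---|---|
| 0.55 | 3 | 0.0526 | 0.5789 |
| 0.55 | 1/3 | 0.1429 | 0.5238 |
| 0.15 | 3 | 0.0370 | 0.1605 |
| 0.15 | 1/3 | 0.2308 | 0.1282 |

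- Same pattern in both arms: 0.5789 − 0.1605 = 41.8 points (k = 3); 0.5238 − 0.1282 = 39.6 points (k = 1/3).
- Opposite patterns: 0.5238 − 0.1605 = 36.3 points; 0.5789 − 0.1282 = 45.1 points.
- k = 1 in both arms leaves 40 points.

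**The same question with no true effect**

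Suppose exclusion is unrelated to response on placebo, 18.5% of the active arm is excluded, and active non-responders are 2 to 3 times as likely as responders to be excluded. At a 40% response rate and ratio 2, the risk in responders is 0.185/(0.4 + 2 × 0.6) = 0.1156, and the retained rate is 0.4 × 0.8844/0.815 = 0.434, a spurious +3.4 points. Ratio 3 gives +5.0. At a 20% rate the shift is +2.0 to +2.8, and at 60% it is +3.9 to +6.1. Taking 10% to 30% exclusion, all cases lie between +1.0 and +11.4. With exclusion unrelated to response in both arms the shift is 0.

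**The case against.** **Only a supportive analysis is touched.** This stands. ITT is principal, and no valid Week 26 scan is dropped from it. A reader might infer that the main Week 26 result is biased; SAP 6 rules that out. Nor do the documents rank the secondary endpoints or call this repeat a robustness check. They give mITT that purpose only for the primary endpoint (Protocol 13.2.1, SAP 9.1.2).

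**Endpoint 13 is not settled.** This also stands. SAP 7.11 refers on to the later analysis sections, and SAP 9.2 names only ITT for the single-visit ANCOVA. For Week 26 change in MRI-PDFF this is a conflict between passages, not a plain instruction to use mITT. The responder endpoint has no such counter-text.

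**The shift is modest.** Largely right. With 97 and 49 subjects retained, the standard error of the assumed difference is √(0.55 × 0.45/97 + 0.15 × 0.85/49) = 0.072. The largest shift, 45.1 − 40 = 5.1 points, is below one standard error. A reader might infer that the repeat cannot be interpreted at all; these figures do not support that. ITT and mITT do share most subjects, however, so a shift of this size could still show as a gap between the two tables.

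**The unused rule is ordinary.** The clause on stopping before Week 20 can never apply in mITT, but neither can the Week 42 histology rule. That is what a completer set does, and the missing-scan clause still operates.

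**A scan-based set already exists.** The interim set (IAmITT) has no 42-week or biopsy condition. It serves the interim analysis only, in about 60 subjects by SAP 6. It is a precedent for the remedy and does not cover the final analysis.

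**Conclusion.** The point holds for the Week 26 responder endpoint. Following SAP 7.11 and Protocol 13.2.2 as written, its mITT repeat drops valid scans because of events usually 16 to 26 weeks later. The effect is a movement of a few points in a supportive estimate (36.3 to 45.1 around a true 40 in the illustration), and only if leaving is related to response.

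The direction is unknown. Protocol 8.3 lists palmar-plantar, visual and respiratory events that can end treatment, and Protocol 5.2 reports dry eye and palmar-plantar events among the commonest on active drug in the earlier China cohort. Arm-related leaving is therefore plausible, but the documents do not show that it tracks the Week 26 response. The rates, the 10% leaving and the factor of 3 are all assumptions.

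For the Week 26 change endpoint the finding is an inconsistency to reconcile. The trial's principal conclusions do not depend on either matter.

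**What to change.** - **SAP 6 and 7.11:** use mITT only for Week 52 endpoints, both histology and MRI-PDFF, so that the Week 52 MRI-PDFF repeat is kept.
- **SAP 6:** define an MRI-evaluable set for the supportive repeat of the Week 26 MRI-PDFF endpoints. It needs a Baseline MRI-PDFF value (at least 8% for the responder endpoint) and an evaluable scan in the Week 20 to 27 window of SAP 7.11. Early Termination scans in that window count, and later discontinuation or a missing biopsy is irrelevant. The gap between endpoint and selection then falls to about one week (27 − 26). An added on-treatment condition is best avoided: SAP 7.11 does not require one of the scan, and it could exclude Early Termination scans.
- **SAP 9.2:** name the populations for the MRI-PDFF responder endpoints and for the Week 26 change endpoint, in agreement with SAP 7.11.
- **SAP 11:** record the departure from Protocol 13.2.2.

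The cost is one set definition and its derivation; no new data are needed and the table layouts can stay. The new set still selects on having a scan, a post-randomization event, so it supports the ITT result and does not replace it. SAP 2 requires the final SAP to be approved before unblinding, so the edit belongs before then.

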13. STATISTICAL CONSIDERATIONS

13.1. Statistical General Considerations

This is a multi-center, randomized, double-blind, placebo-controlled, parallel-design study to evaluate the safety and efficacy of TVB-2640 compared with matching placebo in subjects with NASH.

For “change from Baseline” and “percent change from Baseline” calculations, “Baseline” refers to the last measurement obtained prior to the first administration of study drug. Study Day 1 is the first day of study treatment (TVB-2640 50 mg or placebo). Demographic data (including age, race, ethnicity, sex, height, and weight), medical history, prior treatments, pretreatment clinical characteristics, and other baseline characteristics will be summarized by treatment group and overall.

Descriptive statistics will be displayed by treatment group for all subjects with liver fibrosis stage F2-F3, for all subjects with liver fibrosis stage F1-F3, and for all subjects, as appropriate, to provide an overview of the study results. As appropriate, descriptive statistics will also be displayed by treatment group and by enrollment group. For categorical parameters, the number and percentage of subjects in each category will be presented in data summaries. The denominators for percentages will be based on the number of subjects (n) appropriate for analysis. Continuous variables will generally be summarized based on the following: n, mean, standard deviation, median, minimum, maximum, and standard error of the mean. Categorical data will be summarized using frequency tabulations (number and percentage of subjects).

Demographics and Baseline characteristics (medical histories, physical examinations, and concomitant medications) will be summarized using descriptive statistics for continuous variables and frequency distributions for discrete variables. Study subjects who discontinue the study along with reasons for discontinuation will be summarized and listed. Confidence intervals will be at the 90% and 95% levels. All statistical analyses will be performed using SAS v9.4.

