13.4.2 Analysis Sets

13.4.2.1 Intention-to-Treat Population

The principal analysis of the primary and secondary efficacy endpoints will be based on the Intention-to-Treat (ITT) population, which comprises all randomized subjects; this population will serve as the basis for all efficacy analyses. Subjects' data will be analyzed according to their randomized treatment assignment.

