7. GENERAL DATA HANDLING CONSIDERATIONS

All analyses will be conducted using SAS software Version 9.4 or higher.

All data in the database will be presented in by-subject data listings. Unless otherwise stated, all listings will be sorted by treatment group, center ID, subject number, and assessment date and time, if available.

Unless stated otherwise, continuous data will be summarized by treatment group using descriptive statistics including number of subjects (n), mean, median, standard deviation (SD), first quartile (Q1), third quartile (Q3), minimum (min) value, maximum (max) value.

Unless stated otherwise, categorical data will be summarized by treatment group using counts and percentage based on the number of non-missing values. For selected summaries, the number of missing values will be presented as a separate category with no percentage, if one or more subjects have missing data. Counts of zero will be presented without percentages.

Descriptive statistics will be presented with the following numerical precision:

- Minimum and Maximum: same as the raw data collected
- Mean, Median, Q1, and Q3: one additional decimal place to that reported for Minimum and Maximum
- SD: two additional decimal places than the Minimum and Maximum
- Percentages: reported to one decimal place if percent is <100. If the value is 100, no decimal place will be reported.

Unless otherwise noted, statistical inference will be based on two-sided testing with a 5% significance level. Confidence intervals will be at the 90% and 95% levels.

P-values will be reported to four decimal places. If the value is below 0.0001 it will be noted as < 0.0001; if the value above 0.9999 it will be noted as > 0.9999.

All data up to the time of study completion/withdrawal from the study will be included in the analysis, regardless of duration of treatment.

Numbering for data displays will be based on [International Council for Harmonization \(ICH\) E3](#) whenever possible.

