9.2. Secondary Efficacy Endpoints and Analyses

Secondary efficacy analyses for the other histological responder endpoints will be analyzed in the ITT and mITT populations using the methods described for the primary efficacy endpoint.

Secondary efficacy analyses of endpoints expressed as percent change or change from Baseline only at Week 26 or only at Week 52 will be analyzed in the ITT analysis set using an analysis of covariance (ANCOVA) model with fixed effects for T2DM status at baseline (Yes, No) and treatment group, and a covariate term for baseline analysis value of response. Least squares (LS) means for the percent change from Baseline by treatment and the associated standard errors, the

LS means for the difference between treatment groups, and the associated two-sided 95% CIs and two-sided p-values, based on t-tests, will be derived from the ANCOVA model.

For secondary endpoints assessed at multiple visits, a linear mixed-effects model for repeated measures (MMRM) may be used. The model will include T2DM status at baseline (Yes, No), treatment group, visit, and treatment-by-visit interaction as the fixed effects, and baseline value as a covariate, and the model will use an unstructured variance-covariance matrix. The point estimates for the least-squares mean of the difference treatment groups at each visit and the corresponding 95% confidence interval and two-sided p-value will be summarized. If convergence problems arise when fitting the model, a spatial power covariance structure will be used as a first step. If the model still has convergence issues, compound symmetry covariance structure will be employed. The Kenward-Roger correction for the denominator degrees of freedom will be applied.

ALT, AST, ALP, and GGT will also be summarized in shift tables of baseline to each visit based on range categories of low (below lower limit of normal [LLN], normal, and high [above upper limit of normal [ULN]]).

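### MRI-PDFF responder endpoints 2, 3 and 4 are analysed in all randomised subjects, which does not match their objective (subjects with at least 8% liver fat at Baseline); the interim set's 8% condition is also written the wrong way round

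*SAP*

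**What the plan says.** **Denominator.** SAP 6 defines the ITT population as one that "comprises all randomized subjects; this population will serve as the basis for all efficacy analyses". Protocol 13.4.2.1 agrees: "The principal analysis of the primary and secondary efficacy endpoints will be based on the Intention-to-Treat (ITT) population, which comprises all randomized subjects". Protocol 13.2.2 adds: "The analysis of the primary and secondary endpoints will be carried out for the ITT analysis set and repeated for the mITT analysis set". The same section takes the Week 26 and Week 52 MRI-PDFF ≥30% responder endpoints by name and gives each an analysis like that of the primary endpoint. The Protocol Synopsis bases the secondary analyses on ITT and carries over the primary imputation rule where it applies.

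**Missing scans.** Under SAP 7.11, a subject who "does not provide an MRI-PDFF assessment between Week 20 through Week 27, or who otherwise has missing data will be considered a non-responder" at Week 26. There is a parallel rule for Week 52, and both extend to the ≥50% responder analysis. The section also states: "Imputed data will be analyzed using both the ITT and mITT populations".

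**Objective and endpoint.** SAP 3.2 and Protocol 6.1.2 frame the objective as a proportion among subjects with at least 8% liver fat at Baseline. SAP 5.1 places the 8% condition inside the definition of a responder.

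**Analysis section.** SAP 9.2 says: "Secondary efficacy analyses for the other histological responder endpoints will be analyzed in the ITT and mITT populations". It names ITT for change-from-Baseline endpoints measured at a single visit. It names no set for the MRI-PDFF responder endpoints.

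**Interim set.** The Protocol Synopsis, Protocol 13.4.2.2 and SAP 6 all write the IAmITT condition as 8% ≥ MRI-PDFF. The interim trigger and endpoint in SAP 4.5 require MRI-PDFF ≥ 8%.

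**The concern.** The objective asks what proportion of subjects with enough liver fat at Baseline achieve the reduction. The analysis as written answers a different question, because its denominator includes two groups who cannot respond whatever the drug does:

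- subjects with no baseline scan, for example at sites where MRI-PDFF is not performed (Protocol Table 2, footnote t);
- subjects below 8% at Baseline.

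The second group is foreseen. The inclusion criteria set no minimum MRI-PDFF, and SAP 7.2 plans a Yes/No subgroup on liver fat ≥8% at Baseline. Both groups are scored as treatment failures.

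At stake are the reported rates and the treatment difference for endpoints 2, 3 and 4, and for exploratory endpoint 25, which uses the same responder definition. The mITT repeat does not help, because mITT is defined by treatment duration and histology.

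The IAmITT condition, taken literally, selects subjects at or below 8%. Of these, only a subject at exactly 8% could also meet the responder definition.

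**Working it through.** **1. The plan's own figure.** The only sample size given is for the primary endpoint (Protocol 13.5, SAP 4.3): 40% vs 20%, one-sided 0.05, 80% power, 2:1, 18.5% dropout. With unpooled variance:

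n(placebo) = (0.2 × 0.8 + 0.4 × 0.6 / 2) × (1.645 + 0.842)² / 0.2² = 43.28, so 44; total 3 × 44 = 132; 132 / (1 − 0.185) = 161.96, so 162.

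This reproduces N = 162. No MRI-PDFF quantity enters it. The documents give no expected rate or power for endpoints 2, 3 and 4.

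**2. Dilution.** Let f be the share of randomised subjects without a qualifying baseline scan (none, or below 8%), equal in both arms. A rate p in the restricted set becomes p(1 − f) among all randomised subjects, so the difference is also multiplied by (1 − f).

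**3. Power, illustrative.** Assumptions: 45% vs 20% in the restricted set, and f as tabulated. Test: two-proportion z-test, two-sided 0.05 (SAP 7.4 lists endpoints 2, 3 and 4 as two-sided), unstratified as an approximation to the planned CMH test. SE0 is the pooled standard error under no difference; SE1 is the unpooled one. Power = Φ[(difference − 1.960 × SE0) / SE1].

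At f = 20%:
- Restricted: n = 108 × 0.8 = 86.4 and 54 × 0.8 = 43.2. SE0 = 0.0898, SE1 = 0.0810. (0.25 − 1.960 × 0.0898) / 0.0810 = 0.913, power 81.9%.
- All randomised: n = 108 and 54, rates 36% and 16%. SE0 = 0.0759, SE1 = 0.0680. (0.20 − 1.960 × 0.0759) / 0.0680 = 0.754, power 77.5%.

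| f (assumed) | Restricted: difference, power | All randomised: rates, difference, power |
|---|---|---|
| 5% | 25 points, 88.3% | 42.75% vs 19.0%, 23.75 points, 87.4% |
| 10% | 25 points, 86.4% | 40.5% vs 18.0%, 22.5 points, 84.5% |
| 20% | 25 points, 81.9% | 36.0% vs 16.0%, 20.0 points, 77.5% |
| 40% | 25 points, 69.1% | 27.0% vs 12.0%, 15.0 points, 59.4% |

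With assumed rates of 60% vs 20% and f = 20%, power is 99.7% vs 99.0%.

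**4. If f is not balanced.** Suppose 80% of the drug arm and 70% of the placebo arm have a qualifying baseline scan, and the true response rate is the same in both. The all-randomised analysis then shows a spurious difference of 0.20 × (0.80 − 0.70) = 2 points at a common rate of 20%, and 0.40 × 0.10 = 4 points at 40%. With the imbalance reversed, the sign reverses.

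**5. IAmITT.** This needs no arithmetic. The condition as written in three places gives MRI-PDFF ≤ 8%, while SAP 4.5 needs MRI-PDFF ≥ 8%.

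**The case against.** The strongest reply is that the plan is already determinate and conservative. The passages quoted above all lead to ITT with missing scans as failures, and silence in SAP 9.2 does not displace the general rule in SAP 6. Where the SAP wants a restriction to subjects with at least 8%, as for several subgroups in SAP 7.2, it says so. On that view, no new set is needed.

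Most of this stands. A reader might infer that the denominator is simply left open, pointing to Protocol 13.1 ("denominators for percentages will be based on the number of subjects (n) appropriate for analysis") and SAP 7 ("counts and percentage based on the number of non-missing values"). The documents do not support that. The Protocol 13.1 sentence sits among rules for descriptive summaries and names no restricted set. The SAP 7 rule applies only unless stated otherwise, and 7.11 states otherwise. A reader might also see a gap for scans skipped because of hardship, but 7.11 already covers any scan not provided.

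The reply does not answer the mismatch with the objective. A determinate rule that scores subjects outside the target group as failures still estimates something else.

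It is also fair that f may be small. MRI contraindications are excluded (exclusion criterion 33), and entry requires a steatosis score of at least 1 and, where measurable, CAP ≥ 280 dB/m. Nothing in the documents supports a value as high as 40%.

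**Conclusion.** The point holds, as minor. Followed as written, endpoints 2, 3 and 4 are analysed in all randomised subjects, and their estimates do not answer the stated objective. Under the 45% vs 20% assumption, the cost is under 1 point of power at f = 5% and 4.4 points at f = 20%, with the difference falling from 25 to 20 points in the latter case. Rates and f are assumptions; only the factor (1 − f) follows from the rules themselves, and it needs f to be equal in both arms.

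A reader might infer that this favours the drug or weakens the trial's main conclusion. Neither follows. With balanced f the dilution is conservative. SAP 7.3 provides no further multiplicity control, so these endpoints gate nothing. The primary analysis and N = 162 do not depend on MRI-PDFF.

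The IAmITT inequality is wrong as written, but the trigger and endpoint in SAP 4.5 make the intended direction clear, so it is a wording correction.

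**What to change.** 1. In SAP 6 and 9.2, define the denominator for endpoints 2, 3 and 4, and for the MRI responder part of endpoint 25, as all randomised subjects whose Baseline MRI-PDFF is at least 8%, analysed as randomised. Take Baseline as the last pre-dose value, as in SAP 7.6.
2. Apply the 7.11 non-responder rule to missing post-baseline scans within that set.
3. Restrict the mITT repeat in the same way.
4. Keep the all-randomised ITT version as a sensitivity analysis.
5. In SAP 6, correct the IAmITT condition to MRI-PDFF ≥ 8%, and note the matching protocol correction in SAP 11.
6. Record the denominator change in SAP 11 before unblinding.

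The cost is SAP wording and a second run of the same analysis, with no new data. Because membership is fixed before dosing, the randomised comparison is kept within the set. The downside is a smaller denominator: about 86 and 43 instead of 108 and 54 at an assumed f of 20%.
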